Secondary outcome measures to examine how dentofacial, patient and practitioner characteristics influence a) treatment recommendations suggested by the orthodontists and b) acceptance of treatment recommendations by the patient include the following:

- Practitioner treatment recommendations include the practitioner's general strategies for openbite treatment (from practitioner characteristics form, e.g., whether and how often surgery is recommended), treatment recommendations (e.g. surgical option) presented to the patient, and patient's treatment goals (practitioner perspective);
- Patient acceptance of treatment recommendations includes the patient's self-report of the primary (ideal) treatment plan, whether or not the plan was accepted and why, and the patient's treatment goals;
- Dentofacial characteristics will be ascertained through examination and include: dental or skeletal nature of the openbite, millimetric measure of AOB, and amount of crowding;
- Patient characteristics include age, race, sex, insurance, and education; and
- Practitioner characteristics include the following: age, race, sex, years since received orthodontic training and orthodontic program.

Secondary outcome measures to examine how treatment modalities are associated with treatment success and patient satisfaction at the end of active treatment include the following:

- Treatment success is described above for the primary objective.
- Treatment modalities: Which teeth were extracted, if any; which if any of four treatment modalities were used (surgical component, fixed appliances, removable aligners, and/or TADs (mini-screws, mini-plates)).
- Patient satisfaction: The primary satisfaction measure will be overall satisfaction with treatment, (and secondarily, satisfaction with esthetics and function separately), ascertained by patient report at the end of active treatment.
- Other factors of interest for each include dentofacial characteristics (molar class, crowding, facial pattern, magnitude (millimeters) of overbite), practitioner characteristics (age, race, sex, years since received orthodontic training) and patient characteristics (age, race, sex, insurance, education, treatment

preference (whether patient agreed with primary recommendation), and patient treatment goal).

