Secondary outcome measures to examine how retainer regimens, as well as treatment modalities, dentofacial, patient and practitioner characteristics are associated with treatment stability and patient satisfaction one year after the end of active treatment include the following:

- Treatment stability is described above for the primary objective.
- Retainer regimens include: Type (Hawley, Essix, bonded), whether full-time or part-time (nights only) and compliance with these recommended regimens (ascertained through practitioner and, separately, patient self-report).
- Patient satisfaction: Overall satisfaction with retainers (and secondarily, satisfaction with esthetics and function separately), all of which will be ascertained by patient report at one year after end of active treatment.
- Other factors of interest for each include success of treatment at end of active treatment, and as described above, dentofacial characteristics (molar class, crowding, facial pattern, magnitude (millimeters) of overbite), treatment modalities (extraction, then surgical component, fixed appliances, removable aligners, TADs), practitioner characteristics (age, race, sex, years since received orthodontic training) and patient characteristics (age, race, sex, insurance, education, treatment preference (whether agreed with primary recommendation), and treatment goal).

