4 STUDY DESIGN

- This will be a prospective, observational 3.5-year cohort study of patients who are undergoing different types of orthodontic AOB treatment followed by retainers.
- The study population will consist of adult patients who are in active treatment for AOB, and expect to have treatment completed within 24 months of enrollment into the study. Approximately 210 orthodontists or dentists who routinely perform orthodontic treatment (approximately 35 in each of the six National Dental PBRN regions) will participate. Actual enrollment will be based on interest and enrollment into the Network, and likely will vary per region. Each practitioner will be requested to enroll approximately 3 - 8 adult patients in active AOB treatment over an approximate 11 -months enrollment period, with an enrollment goal of approximately 840 adult patients across the National Network. No practitioner will contribute more than 15 patients.
- Retrospective data will be collected to explore patient, practitioner, and dentofacial characteristics that influence the treatment recommendations and the accepted treatment plans for patients with AOB.
- The prospective cohort design will allow the investigation of how patient, practitioner, and dentofacial characteristics affect the success of treatment. The treatment provided to the patients will not be influenced at all by participation in the study.
- In addition, this study will allow the assessment of how treatment modalities, retainer regimens, and patient characteristics are associated with treatment stability and patient satisfaction one year after treatment.
- At each routinely scheduled retainer check visit, the patient will be asked to report on their retainer usage, and the practitioner will also be asked to judge retainer use.
- Patients will be asked again about satisfaction with their retainer regimen, as well as esthetics and function, at one year after treatment.
- Patients will participate in the study for approximately 3 years, on average, the duration of the treatment and follow-up phases. Practitioners' participation in the study will be approximately 3.5 years.

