Patients will complete an End of Active Treatment Form eliciting whether or not AOB was closed, if they were satisfied overall, satisfied with esthetics, satisfied with function, and if they would recommend the treatment they received to a friend if they had similar problem.

Routine visits within the year following end of active treatment. Practitioner will complete a Retainer Use Form based upon clinical history and examination, recording: 1) AOB status and any changes in alignment of upper or lower incisors; 3) assessment of patient's compliance; 4) any retainers and/or regimen changes; and 5) whether any additional adjunctive treatments have been completed since retention began.

Patients will complete a brief Retainer Use Form eliciting whether or not AOB is closed, how much they are wearing upper/lower retainers, and whether or not they are wearing retainers as requested.

Final visit, one year after end of active treatment. Practitioner will complete a Final Visit Form based upon clinical history and examination, recording the same information as on retainer use form and the current molar relationships.

Final intra-oral frontal photographs, one taken in maximum intercuspation, and another one taken with the incisors slightly apart, will be de-identified and uploaded for measurement of overbite. The practitioner will also measure the height of the right maxillary central incisor using the provided metal ruler.

Patients will complete a brief Final Visit Form eliciting whether or not AOB is (still) closed, current usage, if satisfied with retainer experience, satisfied with esthetics, satisfied with function, if they would recommend the treatment received to a friend if they had similar problem, and if satisfied with type of retainers received after treatment.

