Secondary objective #3b will examine how retainer regimens, as well as treatment modalities, dentofacial, patient and practitioner characteristics are associated with patient satisfaction, assessed one year after end of active treatment. The above process will be repeated except the “outcome” will be patient satisfaction at one year after end of active treatment instead of treatment stability. Separate models will be developed for overall or general satisfaction, and for satisfaction with esthetics and with function; all ascertained at one year after end of active treatment. For this objective, whether or not treatment was stable will be analyzed as an independent variable. A high association is expected, namely, more patients will be satisfied when treatment is successful than when not; however, it will not be a 100% (perfect) association. Some patients who are treated successfully will not be satisfied, and in contrast, some patients who are not treated successfully will be satisfied. Quantification of these proportions is of interest, as well as identifying characteristics (treatment modalities, dentofacial, patient and practitioner) that are associated with satisfaction (or dissatisfaction).

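### The one-year models for satisfaction with esthetics and function (objective 3b) leave out the patient's rating of the same item at appliance removal, so an earlier difference between regimen groups can be credited to the retainer regimen

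*Protocol*

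**What the plan says.** Protocol section 7.1 has patients report on the End of Active Treatment Form "if they were satisfied overall, satisfied with esthetics, satisfied with function". On the Final Visit Form they report "if satisfied with retainer experience, satisfied with esthetics, satisfied with function". Section 4 confirms the repeat: "Patients will be asked again about satisfaction with their retainer regimen, as well as esthetics and function, at one year after treatment". Section 7.2 sets one five-point scale for patient satisfaction.

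The overall item changes its object between visits. Section 3.2 defines the measure at removal as "overall satisfaction with treatment, (and secondarily, satisfaction with esthetics and function separately)" and the one-year measure as "Overall satisfaction with retainers (and secondarily, satisfaction with esthetics and function separately)".

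For objective 3b, section 11.4.2 repeats the 3a process with one-year satisfaction as the outcome, in separate models for overall satisfaction "and for satisfaction with esthetics and with function; all ascertained at one year after end of active treatment". There are five predictor domains (retainer regimen, treatment modality, dentofacial, patient, practitioner), p-value entry and retention rules, and stability as a further independent variable. The 3a process also includes separate analyses by extraction and by whether the bite was closed at the end of treatment. Section 3.2 opens its list of further factors for the one-year outcomes thus: "Other factors of interest for each include success of treatment at end of active treatment". Satisfaction at removal is on neither list, and no analysis of change in satisfaction is described.

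**The concern.** For esthetics and function, the rating at removal is the value of the outcome just before the retention phase. The recommended retention technique is recorded on the practitioner's form at that same visit, so the rating comes before retainer wear and cannot be a consequence of it.

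Regimen is chosen in routine care. A patient unhappy with esthetics at removal will tend to be unhappy a year later whatever is worn. If such patients are unevenly spread over the regimens, the one-year comparison carries that unevenness forward, and the model may present it as a retainer effect. Differences between patients that persist from one visit to the next also stay in the residual when the earlier rating is absent. At stake is the reading of the regimen contrast in a secondary objective; the primary objectives are not affected.

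**Working it through.** **The plan's own figures.** No figure in the protocol bears directly on this point. The nearest is 110 patients per compared group in section 11.4.1 (20-point difference, 80% power, 5% level, ICC 5%), stated for success and stability, not satisfaction. Base rates are not given. Assuming 40% against 60%, a two-sided test without continuity correction needs 97 per group. The design effect is 1 + (m − 1) × 0.05, which gives 97 × 1.10 = 106.7 for m = 3 patients per practitioner and 97 × 1.15 = 111.5 for m = 4. The figure reproduces approximately, but it says nothing about satisfaction at removal.

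**Items at the two visits (sections 3.2 and 7.1).**

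| Item | At removal | At one year | Same item? |
|---|---|---|---|
| Esthetics | yes | yes | yes |
| Function | yes | yes | yes |
| Overall | with treatment | with retainers | no |

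**Bias, under assumptions not in the documents.** 80% are satisfied at removal and 75% at one year. Regimen A goes to 50% of satisfied patients and to a share q of dissatisfied patients. There is no true regimen effect, and regimen depends on nothing but satisfaction at removal.

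Gap at removal = 0.40/(0.40 + 0.20q) − 0.40/(1 − 0.40 − 0.20q):

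- q = 70%: 0.40/0.54 − 0.40/0.46 = 74.1% − 87.0% = −12.9 points.
- q = 60%: 0.40/0.52 − 0.40/0.48 = 76.9% − 83.3% = −6.4 points.
- q = 50%: 0.40/0.50 − 0.40/0.50 = 0.

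The spurious one-year difference is the gap × D. D is the probability of being satisfied at one year among patients satisfied at removal, minus the same probability among those dissatisfied. It is computed here from a bivariate normal with latent correlation r, cut at 80% and 75%.

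| Latent r | D | q = 70% | q = 60% | q = 50% |
|---|---|---|---|---|
| 0.4 | 0.800 − 0.549 = 0.251 | −3.2 | −1.6 | 0 |
| 0.5 | 0.815 − 0.490 = 0.325 | −4.2 | −2.1 | 0 |
| 0.6 | 0.831 − 0.425 = 0.406 | −5.2 | −2.6 | 0 |
| 0.7 | 0.849 − 0.353 = 0.497 | −6.4 | −3.2 | 0 |

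Within levels of satisfaction at removal the difference is zero. That follows from the set-up and is no independent evidence that adjustment would remove all confounding in practice.

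**False positives.** A separate simulation used no true effect, 110 per group, a 10-point gap at removal, 80% satisfied in the reference group and no clustering. With D = 0.3, 0.5 and 0.7, the unadjusted comparison rejected in 7%, 14% and 22% of runs at a nominal 5%. After adjustment the rate was about 4% to 5%. In the table above, latent r of 0.5 to 0.7 corresponds to D of about 0.3 to 0.5, so the 7% and 14% results are the comparable ones.

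**Precision.** On the same dichotomised outcome, the observed correlation is D × √(0.80 × 0.20)/√(0.75 × 0.25) = D × 0.924. For latent r = 0.4 this is 0.23, and for 0.7 it is 0.46. Squared, adjustment removes about 5% and 21% of the variance. As equivalent sample size, 1/(1 − 0.054) − 1 = 6% and 1/(1 − 0.210) − 1 = 27%. The calculation is linear and supposes no other covariates. The 3b models contain others, so the real gain may be smaller. In a logistic model the gain is in power and need not show as a smaller standard error of the log odds ratio.

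**The case against.** **Part of the mechanism is already handled.** The success strata of 3a carry into 3b through the repeated process, stability enters as an independent variable, and section 3.2 lists success. If regimens differ mainly because treatment ended well or badly, much of the difference is absorbed. This stands and narrows the point to dissatisfaction that remains once success and stability are allowed for. It does not close it, since section 11.4.2 itself expects some successfully treated patients to be dissatisfied and the reverse.

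**The bias is conditional.** A reader might infer that earlier differences will be credited to the retainer. The documents do not support that: nothing in them says that regimen choice follows satisfaction, and with no gap at removal there is no bias.

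**The leading satisfaction outcome has no baseline.** A reader might also take overall satisfaction at removal as the baseline of the one-year overall item. It is not, because one concerns treatment and the other retainers, which cannot be rated before wear. The same-item argument is confined to esthetics and function, which section 3.2 ranks below the overall item.

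**The unadjusted association is a legitimate target.** For modality, dentofacial, patient and practitioner characteristics it may be the better one, since satisfaction at removal may lie on their path. This stands, and it limits the adjustment to the regimen contrast.

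**Covariates can be left to the SAP.** The section is titled as proposed analyses and the list in section 3.2 is open. But the protocol itself fixes the domains, the extra independent variable and the selection thresholds, and it carries success at removal forward but not satisfaction at removal. The choice is made in this document and can be commented on here.

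**Conclusion.** The omission is real, and it matters for the retainer-regimen associations with one-year satisfaction with esthetics and with function. If regimen groups differ in satisfaction at removal beyond success and stability, an unadjusted model can attribute that difference to the regimen. Under the stated assumptions the spurious difference is about 2 to 6 points for a gap of 6 to 13 points and latent r = 0.5 to 0.7, and zero for no gap. The precision loss on the dichotomised outcome is about 5% to 21% of variance for latent r = 0.4 to 0.7. The satisfaction rates, the gap and r are all assumptions.

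Two larger readings should be avoided. Squaring r directly would suggest that 16% to 49% of variance is removed for r = 0.4 to 0.7, but that holds only on a linear scale for the undichotomised rating. Nor is 3b the study's smallest sample: primary objective 2 is assessed at the same visit and is restricted to successfully treated patients, whereas 3b is not. The point is an inexpensive improvement to a secondary analysis.

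**What to change.** In section 11.4.2, objective 3b:

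- For the associations of retainer regimen with one-year satisfaction with esthetics and with function, force the rating of the same item at appliance removal into the model, exempt from p-value selection. Report results with and without it.
- In the overall (retainer) satisfaction model, use overall treatment satisfaction at removal as a related covariate, and say that it is not a baseline value of that outcome.
- Report modality, dentofacial, patient and practitioner associations from the model without this term.

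The rating is already on the End of Active Treatment Form, so no new form, visit or patient burden is needed. The costs are that patients without that form need imputation or drop out of the adjusted model, and that two models are reported for these outcomes.

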12 SOURCE DOCUMENTS AND ACCESS TO SOURCE DATA/DOCUMENTS

Each participating site will maintain appropriate dental and research records for this study, using the principles of GCP and complying with regulatory and institutional requirements for the protection of confidentiality of patients. Each site will permit authorized representatives of NIDCR and regulatory agencies to examine (and when required by applicable law, to copy) research records for the purposes of quality assurance reviews, audits, and evaluation of the study safety, progress and data validity.

The following clinical records will be considered source documents where they are used to complete case report forms (CRFs): clinical and office charts, memoranda, recorded data from automated instruments, cephalometric x-rays, and intra-oral frontal photographs of the patient's teeth.

The following CRFs or portions of CRFs will be considered source documents: Practitioner Characteristics Form, Patient's and Practitioner's Enrollment Visit Forms, Patient's and Practitioner's End of Active Treatment Forms, Patient's and Practitioner's Retainer Use Forms, and Patient's and Practitioner's Final Visit Forms.

All study source documents must be maintained in a secure manner, and practice personnel and network personnel will have access to source documents. Study source documents may include clinical records and as such are subject to Health Insurance Portability and Accountability Act (HIPAA) regulations. These records will be subject to examination and copying as stated in this section.

13 QUALITY CONTROL AND QUALITY ASSURANCE

For the Quality Assurance (QA)/Quality Control (QC) activities associated with data collection and processing, the CC will develop a DMP in which the specific data QA/QC procedures will be provided and a Quality Management section in the MOP to further detail the QA/QC process. In the DMP, the procedures will include the development of automatic data quality checks in the database system and the processes related to the data manual review, discrepancy management, delinquent data handling, data updates, data verification and approval, and database audit. A work instruction will be provided to the RCs at the RAS with the specified tasks, timelines of completing the tasks, roles and responsibilities.

The MOP will detail a QA/QC process associated with data collection on paper CRFs (pCRFs) that will include quality checks at the participating practices, followed by QA/QC review at the RAS prior to and after data entry into the web system. Data entered into the system will be compared against pCRFs. The RAS staff will ensure that discrepancies generated by the system are resolved in a timely fashion based on study requirements. The RAS staff will work with practitioners to clarify any data issues and maintain a tracking log for the data changes. The Data Manager at the CC will work with the RCs to ensure that all procedures are followed and that the data are checked according to the validation requirements specified from the study protocol. At the end of the study, the RCs will ensure that all data collected by the regional offices are entered and cleaned. The Data Manager at the CC will verify the completion of data entry and clarifications by running monitoring reports. Once confirmed that the data entry are complete and the data are verified and approved for accuracy, the database will be locked for final analysis. During the study period, when interim data analysis is needed, the Data Manager will coordinate the activities with the RCs and the Statistician. The interim datasets will be provided with the data collected as of the specified date. The data in those datasets will be cleaned if possible but may contain pending issues, which will be provided to the Statistician if requested. The datasets will be provided to the Statistician via secure data transfer method.

The cephalometric x-rays and intra-oral frontal photographs obtained as part of routine orthodontic care before treatment and at the time of appliance removal will be used for this research. Practitioners will obtain an additional intra-oral frontal photograph at the time of appliance removal and two other intra-oral frontal photographs at the Final Study Visit (approximately one year after appliance removal/end of active treatment). Practitioners will be asked to de-identify the x-rays and photos and upload them electronically to a central data collection site created and maintained by the CC. De-identification procedures will be detailed in the Practice Training Manual. The RCs will be asked to verify that x-rays and photographs uploaded are de-identified and of good quality. At the end of each data collection period, the SPI or designee will review the x-rays and photographs to measure overbite, mandibular plane angle, and incisor angulation. The related quality management procedures will be specified in the MOP. The measurements obtained will be used to assess the study outcome measures.

14 ETHICS/PROTECTION OF HUMAN SUBJECTS

14.1 Ethical Standard

The investigator will ensure that this study is conducted in full conformity with the principles set forth in The Belmont Report: Ethical Principles and Guidelines for the Protection of Human Subjects of Research, as drafted by the US National Commission for the Protection of Human Subjects of Biomedical and Behavioral Research (April 18, 1979) and codified in 45 CFR Part 46.

